7.0 STUDY DESIGN AND RULES FOR DOSE ESCALATION

This is a single center phase I/II trial that consists of dose escalation (phase I portion), followed by expanded enrollment at the MTD (phase II portion). Registration and assignment to the dose level will be done at City of Hope (see section 11.0). The rules for dose escalation, dose expansion and termination of escalation are given in sections 7.1 and 7.2. Study design considerations and targeted response rates for the phase II portion of the trial are given in sections 10.2-10.4.

The goal of the phase I study is to evaluate the toxicity results for the combination of intensity modulated radiation therapy (IMRT) with IV busulfan [targeted to AUC (area under curve) of 700-900] and VP-16 as a preparative regimen for hematopoietic stem cell transplantation from an HLA-identical sibling or HLA-fully-matched unrelated donor. For the phase I portion of the study, the assessment will be done in two strata:

- Stratum 1: Adult patients (≥18 years, ≤55 years) with advanced myeloid malignancies or high-risk myelodysplasia.
- Stratum 2: Pediatric patients (6-17 years) with advanced myeloid malignancies or high-risk myelodysplasia.

The primary endpoint for the phase I portion of the study is the determination of the MTD in five doses to be tested in each of the above stratum.

7.1 Dose limiting toxicity (DLT)

Toxicities will be recorded using two distinct grading systems; the modified Bearman Scale (Bearman, S., et al, JCO, Vol 6, No 10 (Oct), 1988, pp1562-1568. See appendix X for details.) and the NCI CTCAE 3.0 Scale.

Generally, the modified Bearman Scale will be used to define DLT events and the CTCAE 3.0 Scale will be used for reporting adverse events. The only exceptions relate to defining hematologic DLT events, for this the CTCAE 3.0 Scale will be used, and for capturing veno-occlusive disease (**VOD**), for this the CTCAE 2.0 Scale will be used. (The NCI CTCAE 3.0 and 2.0 can be found at http://ctep.cancer.gov/reporting/ctc.html.) To be evaluable for toxicity, a patient must start treatment and be observed for at least 30 days following the completion of the transplant procedure or have experienced DLT. All patients who are not evaluable for toxicity will be replaced. No dose escalation will occur until DLT evaluations are complete for all patients on a dose level.

As mentioned dose limiting toxicities (DLTs) will be graded according to the modified Bearman Scale. Dose limiting toxicity (DLT) in a given patient is defined as: any grade 3 or 4 toxicity per the modified Bearman Scale (appendix X). Hematologic DLT is defined as: grade 4 neutropenia associated with fever or infection and lasting beyond three weeks, or grade 4 neutropenia lasting for more than 28 days per CTCAE 3.0 toxicity criteria.

The maximum tolerated dose (MTD) is defined as the highest dose tested in which fewer than 33% of patients experienced DLT attributable to the study treatment when at least six patients were treated at the dose and are evaluable for toxicity. The MTD is one dose level below the DLT level. At least six patients will be treated at the MTD. If the MTD does not satisfy these conditions, no expansion at the MTD will occur, as the treatment will be considered lacking adequate safety.

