7.2 Dose Escalation Schedule: IMRT

The initial dose level will be 1200 cGy, with dose escalation according to the schedule below.

- 1. 1200 cGy = 150cGy x 8 doses
- 2. 1350 cGy = 150cGy x 9 doses
- 3. 1500 cGy = 150cGy x 10 doses
- 4. 1750 cGy = 175cGy x 10 doses
- 5. 2000 cGy = 200cGy x 10 doses

Three patients will be treated at each new dose level. If 0/3 patients experience DLT, 3 patients will be treated at the next dose level. If DLT attributable to the study treatment is experienced in exactly 1/3 patients, 3 more patients (for a total of 6) will be treated at that dose level. If no additional DLT is observed at the expanded dose level (e.g., 1/6 with DLT), the dose will be escalated. Escalation will terminate as soon as two or more patients experience any DLT attributable to the study treatment, at a given dose level. The Phase I trial will be closed when 6 patients have been treated at the next lower dose level, and at most 1/6 patients experience DLT. If more than 1/6 patients experience DLT, the next lower dose will be expanded. There will be no dose escalation within a patient.

The two strata will proceed independently through the dose escalation with the following exceptions: no pediatric patients are to be enrolled on dose level 1 until the adult stratum has been escalated to dose level 2. No pediatric patients will be enrolled to dose level 2 until dose level 2 has been determined to be safe in the adult population, and the same is true for levels 3, 4 & 5.

7.3 Design considerations for a phase II trial.

All patients accrued to the MTD dose level will be included in the response assessment for the phase II portion of the trial.

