10.3 Phase II Monitoring

Early stopping rules are incorporated into the phase II portion of the study for excessive toxicity. However there will be no interim analysis for efficacy during the phase II stage. Toxicities will be recorded using two distinct grading systems; the modified Bearman Scale (Bearman, S., et al, JCO, Vol 6, No 10 (Oct), 1988, pp1562-1568. See appendix X for details.) and the NCI CTCAE 3.0 Scale.

Generally, the modified Bearman Scale will be used to define (grade) 'early stopping' events (toxicities), and the NCI CTCAE 3.0 Scale will be used for reporting adverse events. The only exception relates to how hematologic toxicities are graded and incorporated into the early stopping criteria. For hematologic toxicities the CTCAE 3.0 Scale will be used. The table below will be consulted as relevant toxicities are encountered, so there will be no accrual-based interim analysis point.

Early Stopping Criteria: For each adverse outcome, stop if the cumulative number of patients reaches or exceeds the following limits:

Table of Early Stopping C	Criteria				
# of patients treated at the MTD	# of patients expired due to treatment	# of patients with grade 3 toxicities that would require an	Probability stopping r given a fa	ule will be	invoked
	related causes that would stop the study*	evaluation for safety per Bearman Scale**	10%	15%	20%
12	3	3	0.11	0.26	0.45
18	5	5	0.12	0.27	0.47
24	6	6	0.12	0.31	0.53
30	8	8	0.13	0.31	0.53

36	9	9	0.13	0.32	0.55
* Note: The stopping rules are	not statistically based; expec	ted treatment related mortalit	y should not	to exceed 2	5%.

** Note: For hematologic toxicities: Any grade 4 neutropenia associated with fever or infection and lasting beyond three weeks, or grade 4 neutropenia lasting for more than 28 days per CTCAE 3.0 toxicity criteria should be counted toward the early stopping rule.

Any patient who receives treatment as part of the phase II portion of this protocol will be evaluable for toxicity. Each patient will be assessed periodically according to the treatment schedule for the development of any toxicity. The toxicity rule for safety will be assessed as each patient reaches day +30 post transplantation. If more than the specified number of patients (noted in the table above) have significant treatment related toxicities, then the safety of the study will be evaluated.

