Appendix IX: Modified Bearman Scale

	Grade I	Grade II	Grade III
Cardiac toxicity	Mild EKG abnormality, not requiring medical intervention; or noted heart enlargement on chest x-ray with no clinical symptoms	Moderate EKG abnormalities requiring and responding to medical intervention; or requiring continuous monitoring without treatment; or congestiveheart failure responsive to digitalis or diuretics	Severe EKG abnormalities with no or only partial response to medical intervention; or heart failure with no or only minor response to medical intervention; or decrease in voltage by more than 50%
Bladder toxicity	Macroscopic hematuria after 2 days from last chemotherapy dose with no subjective symptoms of cystitis and not caused by infection	Macroscopic hematuria after 7 days from last chemotherapy dose not caused by infection; or hematuria after 2 days with subjective symptoms of cystitis not caused by infection	Hemorrhagic cystitis with frank blood, necessitating invasive local intervention with installation of sclerosing agents, nephrostomy or other surgical procedure
Renal toxicity	Increase in creatinine up to twice the baseline value (usually the last recorded before start of conditioning)	Increase in creatinine above twice baseline but not requiring dialysis	Requirement of dialysis
Pulmonary toxicity	Dyspnea without chest x-ray changes not caused by infection or congestive heart failure; or chest x-ray showing isolated infiltrate or mild interstitial changes without symptoms not caused by infection or congestive heart failure	Chest x-ray with extensive localized infiltrate or moderate interstitial changes combined with dyspnea and not caused by infection or CHF; or decrease of PO2 (> 10% from baseline) but not requiring mechanical ventilation or > 50% O2 on mask and not caused by infection or CHF	Interstitial changes requiring mechanical ventilatory support or > 50% oxygen on mask and not caused by infection or CHF

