Hepatic toxicity	Mild hepatic dysfunction with bilirubin $\geq 2.0 \text{ mg/dL}$ and $\leq 6.0 \text{ mg/dL}$ or weight gain $> 2.5\%$ and $< 5\%$ from baseline, of non-cardiac origin; or SGOT increase more than 2-fold but less than 5-fold from lowest preconditioning	Moderate hepatic dysfunction with bilirubin > 6.0 mg/dL and < 20 mg/dL; or SGOT increase > 5-fold from preconditioning; or clinical ascitis or image documented ascitis > 100 mL; or weight gain > 5% from baseline of non- cardiac origin	Severe hepatic dysfunction with bilirubin > 20 mg/dL; or hepatic encephalopathy; or ascitis compromising respiratory function
CNS toxicity	Somnolence but the patient is easily arousable and oriented after arousal	Somnolence with confusion after arousal; or other new objective CNS symptoms with no loss of consciousness not more easily explained by other medication, bleeding or CNS infection	Seizures or coma not explained (documented) by other medication, CNS infection, or bleeding
Stomatitis	Pain and/or ulceration not requiring a continuous IV narcotic drug	Pain and/or ulceration requiring a continuous IV narcotic drug (morphine drip)	Severe ulceration and/or mucositis requiring preventive intubation; or resulting in documented aspiration pneumonia with or without intubation
GI toxicity	Watery stools > 500 mL but < 2,000 mL every day not related to infection	Watery stools > 2,000 mL every day not related to infection; or macroscopic hemorrhagic stools with no effect on cardiovascular status not caused by infection; or subileus not related to infection	Ileus requiring nasogastric suction and/or surgery and not related to infection; or hemorrhagic enterocolitis affecting cardiovascular status and requiring transfusion

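### In phase I, a treatment-related death before day 30 without a listed DLT is replaced rather than counted, so it leaves the 3+3 and MTD counts and can bias the MTD upward

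*Combined protocol and SAP*

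**What the plan says.** Evaluability and replacement in phase I are set in section 7.1: "To be evaluable for toxicity, a patient must start treatment and be observed for at least 30 days following the completion of the transplant procedure", with prior DLT as the only alternative route. The section then states: "All patients who are not evaluable for toxicity will be replaced". No reason for being non-evaluable is exempted.

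A non-hematologic DLT is "any grade 3 or 4 toxicity per the modified Bearman Scale (appendix X"). A hematologic DLT is grade 4 neutropenia lasting more than three weeks with fever or infection, or more than 28 days in any case. Neither definition mentions death.

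The printed scale is Appendix IX, and its columns stop at grade III. The appendix X that 7.1 cites is the list of time points for grading. Three grade III entries exclude infection:

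- Pulmonary: "Interstitial changes requiring mechanical ventilatory support or > 50% oxygen on mask and not caused by infection or CHF".
- CNS: "Seizures or coma not explained (documented) by other medication, CNS infection, or bleeding".
- GI, for the ileus limb only: "Ileus requiring nasogastric suction and/or surgery and not related to infection; or hemorrhagic enterocolitis affecting cardiovascular status and requiring transfusion".

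Section 7.2 escalates on 0/3 or 1/6 and ends escalation once two patients at a level have an attributable DLT. The MTD in 7.1 requires fewer than 33% with DLT among at least six evaluable patients.

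Phase II is handled differently in section 10.3: "Any patient who receives treatment as part of the phase II portion of this protocol will be evaluable for toxicity". That section also tabulates a limit on treatment-related deaths.

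**The concern.** An early treatment-related death is the outcome an escalation rule most needs to see. Under 7.1 it is seen only if the patient first met a listed DLT. Three routes can miss:

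- A fatal infectious pneumonia is outside the pulmonary item.
- A fatal CNS infection or intracranial bleed is outside the CNS item.
- A septic death before three weeks of grade 4 neutropenia is outside the hematologic definition, unless another organ item was met.

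Each such patient is replaced by someone who may have no DLT, and the death then contributes nothing to the level's numerator or denominator.

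The MTD uses the same evaluable patients, and phase II treats adults at that dose. The adult result also gates the pediatric stratum: "No pediatric patients will be enrolled to dose level 2 until dose level 2 has been determined to be safe in the adult population", with the same condition at levels 3 to 5. An adult level passed in error would carry over.

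**Working it through.** **The plan's own figure.** Section 10.1 expects 18 patients per stratum if the top level is well tolerated. Five levels × 3 patients, plus 3 more to reach six at the top level, gives 15 + 3 = 18. This matches, so the rule is being read as the plan intends.

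**A case needing no assumed rate.** Two of the first three patients at a level die before day 30 of treatment-related causes without a listed DLT. The third patient and the two replacements have no DLT. Under 7.1 the level scores 0/3 and the dose is escalated. With the deaths counted as events it scores 2/3 and escalation terminates.

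**Inputs for the general case.** Both are assumptions; the documents give neither.

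- q: rate of attributable listed DLT.
- d: rate of treatment-related death before day 30 without a listed DLT, disjoint from q.

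**Event rate the 3+3 sees.**

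- Deaths replaced: p = q/(1 − d).
- Deaths counted: p = q + d.
- Difference: (q + d) − q/(1 − d) = d(1 − q − d)/(1 − d), which is positive whenever d > 0 and q + d < 1.

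**Chance of escalating past one level (7.2).** P = (1 − p)³ + 3p(1 − p)⁵, which falls as p rises. The direction of the bias is therefore fixed.

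Worked line for q = 0.10, d = 0.05:

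- Replaced: p = 0.10/0.95 = 0.1053, so P = 0.716 + 0.181 = 0.897.
- Counted: p = 0.15, so P = 0.614 + 0.200 = 0.814.

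**Results, replaced / counted.** P(≤1/6) is the binomial chance of passing the six-patient check at the MTD.

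| d | p (q = 10%) | P(escalate), q = 10% | P(≤1/6), q = 10% | P(escalate), q = 20% |
|---|---|---|---|---|
| 1% | 0.101 / 0.11 | 0.904 / 0.889 | 0.884 / 0.866 | 0.704 / 0.687 |
| 3% | 0.103 / 0.13 | 0.901 / 0.853 | 0.880 / 0.822 | 0.695 / 0.643 |
| 5% | 0.105 / 0.15 | 0.897 / 0.814 | 0.875 / 0.776 | 0.686 / 0.600 |
| 10% | 0.111 / 0.20 | 0.887 / 0.709 | 0.863 / 0.655 | 0.660 / 0.494 |

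**Over the whole escalation.** All five levels were simulated, with de-escalation, 100,000 trials per case. Listed-DLT rates were assumed to be 5, 10, 15, 20 and 25%, with d = 5% at every level. The mean selected level is 3.22 with replacement and 2.57 with deaths counted. Level 5 is selected in 24.1% and 13.3% of trials. With d = 0 the two rules agree apart from simulation error (mean level 3.32 under both).

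**Chance that the issue arises.** Among 18 treated patients, P(at least one such death) = 1 − (1 − d)¹⁸, which is 0.17 at 1%, 0.42 at 3% and 0.60 at 5%.

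**The case against.** Five points can be made for the plan.

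1. **Grade 4 may mean fatal.** Grade III already covers dialysis, ventilation and coma, so a higher grade reads most naturally as fatal toxicity. On that reading a fatal organ toxicity is a DLT and the patient is evaluable. The reading is plausible, but the documents do not state it. Even if it is right, they do not say whether a death from an infection or bleed excluded at grade III would be graded at all.

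2. **The gap is narrow.** The cardiac, renal, hepatic, bladder and stomatitis items and the hemorrhagic enterocolitis limb carry no infection exclusion, and grade III stomatitis names aspiration pneumonia. Section 7.1 also captures veno-occlusive disease through CTCAE 2.0. Many septic or multi-organ deaths would therefore count. This stands, and it makes the 10% row an upper illustration rather than an expectation.

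3. **The two-deaths case is rare.** Two such deaths in the first three patients has probability 3d²(1 − d): about 0.03% at 1%, 0.3% at 3% and 0.7% at 5%. This also stands. The case shows how the rule works, and one death can still change a decision: 0/3 escalates at once, whereas 1/3 requires three more patients.

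4. **Oversight exists.** Escalation waits for complete DLT evaluations, the DSMB receives data after each level, deaths are reported as SAEs, and the section 10.3 death limit is indexed to patients treated at the MTD. These are real safeguards, but none puts a replaced death back into the 3+3 count. The first row of the death table is at 12 patients, while escalation decisions use three to six.

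5. **Adult escalation may be finished.** Section 10.2 mentions 23 patients already treated, 6 to 10 eligible per year and about one and a half years of accrual. That fits seven remaining patients (30 − 23) better than thirty, which would take 3 to 5 years. If so, the amendment cannot change the adult MTD prospectively, and the adult part becomes a retrospective check.

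**Conclusion.** The concern holds. Followed as written, 7.1 removes a treatment-related death before day 30 without a listed DLT from both the escalation count and the MTD count, and section 10.3 treats the same event differently in phase II. The bias can only be upward. Its size cannot be fixed from the documents: it is negligible if about 1% of patients die this way, a loss of roughly 5 to 9 percentage points in the escalation probability at 3 to 5%, and 17 to 18 points at 10%. These figures assume listed-DLT rates of 10 or 20%, disjoint events, and replacements drawn from the same population. If grade 4 is confirmed to mean fatal toxicity, the gap narrows to deaths outside the scale's items. The documents do not show that any such death has occurred or been replaced. It should be fixed, because an escalation rule should not depend on an undefined grade and a wrong appendix reference.

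**What to change.** Amend section 7.1 as follows:

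- Limit replacement to patients who leave observation before day 30 for reasons unrelated to treatment toxicity or treatment-related death.
- Treat a death before day 30 judged attributable to study treatment as evaluable. Enter it as an event in the escalation and MTD counts, and reconcile this with section 10.3.
- Allow deaths judged unrelated to be replaced, so that they do not dilute the DLT rate. Record cause and attribution, on the scale already in section 16.0, before the level is closed.
- State what Bearman grade 4 means and correct the appendix reference here and in section 10.3.

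Separately, list any phase I patients already replaced, with reasons, and recheck the escalation decisions they affected.

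The cost is a short amendment and a brief review of past replacements. Escalation may stop slightly earlier, and a few replacements would no longer be allowed. If adult escalation is complete, the prospective effect falls mainly on the pediatric stratum.

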7.2 Dose Escalation Schedule: IMRT

The initial dose level will be 1200 cGy, with dose escalation according to the schedule below.

- 1. 1200 cGy = 150cGy x 8 doses
- 2. 1350 cGy = 150cGy x 9 doses
- 3. 1500 cGy = 150cGy x 10 doses
- 4. 1750 cGy = 175cGy x 10 doses
- 5. 2000 cGy = 200cGy x 10 doses

Three patients will be treated at each new dose level. If 0/3 patients experience DLT, 3 patients will be treated at the next dose level. If DLT attributable to the study treatment is experienced in exactly 1/3 patients, 3 more patients (for a total of 6) will be treated at that dose level. If no additional DLT is observed at the expanded dose level (e.g., 1/6 with DLT), the dose will be escalated. Escalation will terminate as soon as two or more patients experience any DLT attributable to the study treatment, at a given dose level. The Phase I trial will be closed when 6 patients have been treated at the next lower dose level, and at most 1/6 patients experience DLT. If more than 1/6 patients experience DLT, the next lower dose will be expanded. There will be no dose escalation within a patient.

The two strata will proceed independently through the dose escalation with the following exceptions: no pediatric patients are to be enrolled on dose level 1 until the adult stratum has been escalated to dose level 2. No pediatric patients will be enrolled to dose level 2 until dose level 2 has been determined to be safe in the adult population, and the same is true for levels 3, 4 & 5.

7.3 Design considerations for a phase II trial.

All patients accrued to the MTD dose level will be included in the response assessment for the phase II portion of the trial.

8.0 STUDY CALENDAR

See appendix V for Study Calendar.

9.0 CRITERIA FOR EVALUATION AND ENDPOINT DEFINITIONS

9.1 Criteria for Evaluation: Acute Myeloid Leukemia (AML) and Myelodysplasia (MDS)

Response and progression will be evaluated in this study using the Revised Recommendations of the International Working Group for Diagnosis, Standardization of Response Criteria, Treatment Outcomes, and Reporting Standards for Therapeutic Trials in Acute Myeloid Leukemia [JCO 21:4642-4649, 2003]. The following categories from the Revised Recommendations of the International Working Group will be used:

Morphologic leukemia-free state: Less than 5% blasts in an aspirate sample with marrow spicules and with a count of at least 200 nucleated cells. There are no Auer rods or persistence of extramedullary disease. (The presence of a unique phenotype by flow cytometry identical to what was found in the pre-treatment specimen is viewed as persistence of leukemia.)

Morphologic complete remission (CR): The patient achieves the morphologic leukemiafree state and has an absolute neutrophil count of >1000/uL and a platelet count \geq 100,000/uL. The patient is independent of blood transfusions. No duration of response is required to fulfill these criteria.

Cytogenetic complete remission (CRc): Patients who achieve a morphologic CR along with reversion to a normal karyotype by cytogenetic analysis. For patients who have unique markers by routine cytogenetics or by FISH upon enrollment, these markers will be followed on subsequent bone marrow examinations using the same technique(s) to evaluate for CRc.

Molecular complete remission (CRm): Patients who achieve a morphologic CR with no residual disease by molecular or flow cytometic detection methods. For patients with unique multi-dimensional flow cytometry markers at the time of enrollment, these will be repeated on subsequent bone marrow studies to evaluate for CRm.

Morphologic CR with incomplete blood count recovery (Cri): Patient fulfills the criteria for morphologic CR except for residual neutropenia (<1000/uL) and/or thrombocytopenia (<100,000/uL).

Partial Remission (PR): This requires the same hematologic values for a CR but with a decrease of at least 50% in the percentage of blasts to a post-treatment value of 5% to 25% in the bone marrow aspirate. (If the pre-treatment blast percentage was 50-100%, this must decrease to a value between 5-25%. If the pre-treatment blast percentage was 20-49%, this must decrease by at least half to a value greater than 5%.) A value \leq 5% is also considered a PR if Auer rods are present.

